4.1.6 Time weighted average lipid value

The time-weighted average lipid value is defined as the lipid value multiplied by the number of days since the last lipid assessment, summed for all lipid observations (this includes observations made at unscheduled visits), and divided by the sum of days between all visits. No imputation will be made for lipid missing values for the time-weighted average analysis.

$$\text{TWA} = \frac{x_1 t_1 + x_2 t_2 + \dots + x_n t_n}{t_1 + t_2 + \dots + t_n}, \text{ where}$$

x_i s are the lipid values measured at times $i=1, 2, \dots, n$, t_i s are the number of days between visit i and visit $(i-1)$.

And $T = t_1 + t_2 + \dots + t_n$ is the total number of days over which the assessments took place. This will be calculated for both sets of LDL-C values (collected and converted) described in section 4.1.

4.1.7 Summaries of continuous variables

Continuous variables will be summarized using number of observations, mean, SD, median, minimum and maximum, and will be presented by visit when applicable. Summaries for continuous endpoints known to have skewed distributions will also include quartiles and the interquartile range.

Minimum and maximum values will be reported to the same degree of precision as the raw data unless otherwise stated. Mean and median will be reported to one further degree of precision. SD will be reported to two further degrees of precision compared to the raw data.

4.1.8 Summaries of categorical variables

Categorical variables will be summarized with number of observations and percentage of subjects in each category.

4.1.9 Summaries of shifts from baseline in categorical variables

Changes from baseline in certain categorical variables will be summarized using shift tables. Frequencies and percentages of subjects within each treatment group will be generated for levels of cross-classifications of baseline and the on-treatment value of the variable. The on-treatment value can be either the value at a certain time point, or the minimum or maximum value in the direction of toxicity that has been observed during a study period (e.g., laboratory tests). Treatment group differences will not be assessed in summaries of shifts.

4.2 Analysis methods

4.2.1 Subject disposition

A summary of subject disposition will display the number of subjects enrolled, i.e., signed informed consent, as well as the number of subjects randomized and who comprised each analysis set by treatment group and overall. In addition, the number and percent of subjects who completed the study (identified on the eCRF as having completed the study – ‘Was subject prematurely withdrawn from study’ =No), discontinued from the study, and reasons for discontinuation from the study will be summarized by treatment group and overall. An accompanying listing of subjects who prematurely discontinued from the study will be provided.

The exclusions from the PP analysis set will include, but will not be limited to, the subjects who took prohibited concomitant medications, who were non-compliant in taking the investigational product, or who had major deviations of study procedures. These exclusions for the PP analysis set are explicitly defined in Section 2.2 and Appendix A.

A listing will be produced for all enrolled subjects in the ITT analysis set.

4.2.2 Protocol Violations and Deviations

Important protocol deviations will be summarized and listed by treatment group for the ITT analysis set.

4.2.3 Demographic and baseline characteristics

Demographic and other baseline characteristics will be summarized by treatment group and overall, for the ITT analysis set.

Baseline height and weight will be summarized as continuous variables. Sex and race will be summarized as categorical variables. Age at time of informed consent will be summarized as a continuous variable, and by grouping subjects according to age categories (< 65 and ≥ 65 years). Baseline BMI will be summarized as a continuous variable, and by grouping subjects according to BMI categories (< 25 kg/m², ≥ 25- < 28 kg/m² and ≥ 28 kg/m²).

Other baseline characteristics to be summarized are listed in the following table:

Table 1 Summaries of baseline characteristics

Characteristic	Summarized as	Categories
Smoking status	Categorical	Former, Current, Never
Alcohol use	Categorical	Former, Current, Never
China Adult Dyslipidemia Management Guidelines Risk ¹	Categorical	10-year Ischemic cardiovascular disease (ICVD) risk < 5% 10-year ICVD risk ≥ 5% - <10%
CrCl	Continuous	

Characteristic	Summarized as	Categories
CrCl	Normal	CrCl > 80 (ml/min)
	Mild impairment	CrCl 50 – 80 (ml/min)
	Moderate impairment	CrCl 30-<50 (ml/min)
	Severe impairment	CrCl <30 (ml/min)
Maximum IMT (Visit 2 and 3)	Continuous	
Major risk factors for ICVD ²	Categorical	Hypertension
		Smoking
		HDL-C < 40 mg/dL
		Obesity (body mass index $\geq 28\text{kg/m}^2$)
		Family history of premature coronary heart disease (CHD)
		Age Male ≥ 45 years, Females ≥ 55 years)

¹Summary will be provided for both interactive voice/web response system (IxRS) data and electronic case report form (eCRF) data.

² Total number of risk factors (0 - 6) will also be summarised, with a sub-category under 2 risk factors of with/without hypertension.

All summaries of continuous characteristics will be based on non-missing observations. For categorical characteristics, percentages will be calculated out of the total number of subjects in the data set, overall and by treatment group (i.e., each denominator includes the number of subjects with missing/unknown values for the endpoint).

Demographic and baseline disease characteristics will be presented in listings for all randomized subjects.

4.2.4 Medical and surgical history

Medical history will be coded using the latest Medical Dictionary for Regulatory Activities (MedDRA) version available at the time of database lock.

Past and current medical history will be summarized together by system organ class (SOC), preferred term (PT), and treatment group for the ITT analysis set. Surgical histories will be summarized in the same way.

The numbers and percentages of subjects with general medical history findings will be provided using the ITT analysis set. Surgical histories will be summarized in the same way.

Medical and surgical histories will be listed for the ITT analysis set.

4.2.5 Duration of exposure

4.2.5.1 Study therapy

Duration of exposure is defined as the number of days between the start and the end dates of study therapy, where the start date of study therapy is the date of the first dose of investigational drug or placebo, and the end date of study therapy is the last known dose of investigational drug or placebo during the double-blind treatment period, i.e., Duration of exposure = Last dosing date - First dosing date + 1. Duration of exposure, excluding interruptions is defined in the same way, but only days where dose taken is greater than 0 are included.

Duration of exposure will be summarized using all subjects treated (safety analysis set), presenting the numbers and percentages of subjects with a duration of exposure within the following week ranges by treatment group: less than 1 week, 1 to less than 7 weeks, 7 to less than 14 weeks, 14 to less than 21 weeks, 21 to less than 28 weeks, 28 to less than 35 weeks, 35 to less than 42 weeks, 42 to less than 49 weeks, 49 to less than 56 weeks, 56 to less than 63 weeks, 63 to less than 70 weeks, 70 to less than 77 weeks, 77 to less than 84 weeks, 84 to less than 91 weeks, 91 to less than 98 weeks, 98 to less than 104 weeks and 104 weeks or more.

The cumulative exposure will be summarized for all subjects in the safety analysis set and separately for subjects who prematurely discontinued. The numbers and percentages of subjects with duration of exposure of at least the following number of weeks will be presented by treatment group:

Up to 1 week, 1 week or more, 7 weeks or more, 14 weeks or more, 21 weeks or more, 28 weeks or more, 35 weeks or more, 42 weeks or more, 49 weeks or more, 56 weeks or more, 63 weeks or more, 70 weeks or more, 77 weeks or more, 84 weeks or more, 91 weeks or more, 98 weeks or more and 104 weeks or more.

Also, the mean, SD, median and range of duration of exposure (days) will be presented by treatment group for all subjects in the safety analysis set and separately for subjects who prematurely discontinued.

Duration of exposure for the investigational product will be listed by subject using the safety analysis set. Additionally, a listing of subjects by batch number of investigational product will be produced.

4.2.5.2 Prior and concomitant medications

All medications will be coded using the latest AstraZeneca Drug Dictionary at the time of database lock.

Prior medication is defined as medication with a stop date before the date of the first dose of study medication.

A medication will be regarded as concomitant if the start date is on or after the date of first dose, or if it started prior to the date of first dose and was ongoing after the date of first dose.

Concomitant rescue medications will be summarized separately. Partial date imputation for medications is described in Section 4.6.7.

Prior and concomitant medications will be summarized by treatment group for the safety analysis set by drug class (anatomic class and therapeutic class), and generic drug name for each treatment group.

Prior and concomitant medications will be listed together.

Vitamin K antagonists including warfarin derivatives and coumadin will be listed by subject. These will be identified using ATC code B01AA.

4.2.5.3 Treatment compliance

Overall treatment compliance percent is calculated during the double-blind treatment period for the blinded study medication (rosuvastatin 20 mg and placebo) as follows:

$$\text{Compliance (\%)} = \frac{\text{Total number of tablets dispensed} - \text{Total number of tablets returned}}{\text{Last return date} - \text{First dispense date}} \times 100$$

If no tablets have been returned during the treatment period, the compliance will be set to missing (these subjects will also be excluded from the PP analysis set). If a subject does not return study medication at the last visit, the last visit date will be used as the last return date for the compliance calculation. If the number of tablets returned is missing, the subject is assumed to have taken the treatment as prescribed by the CSP. If the return date is missing for a dispensed kit during the treatment period, the return date for that kit will be imputed to the next dispensed date, and the subject is assumed to have taken the treatment as prescribed by the CSP (i.e. 1 tablet per day, to a maximum of the dispensed dose).

Treatment compliance will also be displayed in a listing.

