#### **4.2.11 Early Termination Visit**

The term "early termination" refers to a subject's non-completion of a study whether by his or her own choice or the investigator's decision or due to discontinuation of the study by the Sponsor.

In the absence of a medical contraindication or significant protocol violation, every effort will be made by the principal investigator to keep the subject in the study. Should the subject decide to withdraw, an attempt will be made to conduct an Early Termination (ET) Visit within 1 week of discontinuation of study treatment. The ET visit will include all procedures normally done at Visit 13 (Week 104) except the IMT procedures. A single IMT is to be performed on any subject who withdraws after 26 weeks.

The primary reason for a subject withdrawing prematurely should be recorded on the eCRF.

The investigator should notify the Study Physician promptly when a subject is withdrawn, or if the study is stopped at their site by the Independent Ethics Committee/Institutional Review Board, or if the investigator elects to stop the study.

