4.6 Conventions

4.6.1 Study period start and end dates

Double-blind treatment period

The randomized treatment period is assumed to start at the date of the first randomized double-blind dose, and to end at the last dose of double-blind study drug as recorded in the DOSE CRF module.

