6	
Enrolled, even though subject met the exclusion criteria below:
 
Use of pharmacologic lipid-lowering medications (eg, statins, fibrate derivatives, bile acid binding resins, niacin or its analogues at doses > 400 mg or prescribed Chinese traditional drugs), including cholesterol-absorption inhibitors (CAIs), and CAI/statin combination, within 12 months prior to Visit 1 (Week -6)
	Complete data exclusion.
	Major deviations:	
8	Overall compliance during the double-blind treatment period <80% of the prescribed drug	Complete data exclusion.

Number	Important protocol deviations / Criteria	Complete/partial data exclusion
9	Use of prohibited/disallowed medication during the double-blind treatment period (medications with an ATC code of C10AA, C10, or C10AX or 'Reason for Therapy' is recording on the eCRF as 'Control for dyslipidemia', 'Hyperlipidemia' or 'Hypolipidemic' are only considered disallowed if they are used for more than 3 months across the study period before last dose date).	Partial data exclusion: Data at the affected visit and subsequent visits will be excluded. These concomitant medications are the lipid lowering agents listed in appendix 7.7.1 of the protocol.
10	CIMT data from ultrasound scans taken more than 31 days after the last dose of study medication.	Partial data exclusion: Data at the affected visit and subsequent visits will be excluded.
11	Subject randomly allocated a treatment out of sequence or inadvertently receives the wrong treatment.	Complete data exclusion.

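### The SAP compliance denominator runs to the last tablet return instead of the last dose, so a late return after a permanent stop can remove a subject's on-drug scans from the per-protocol analysis

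*SAP*

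**What the plan says.** **Formula.** SAP 4.2.5.3 defines one overall percentage for the double-blind treatment period: tablets dispensed minus tablets returned, divided by the last return date minus the first dispense date. The last dose date does not appear. Two fallback rules follow. For non-return: "If a subject does not return study medication at the last visit, the last visit date will be used as the last return date". For a missing count: "If the number of tablets returned is missing, the subject is assumed to have taken the treatment as prescribed by the CSP".

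**Period.** SAP 4.6.1 takes the randomized treatment period to start at the first dose and "to end at the last dose of double-blind study drug as recorded in the DOSE CRF module". SAP 4.2.5.1 uses the same end point for exposure: "Duration of exposure = Last dosing date - First dosing date + 1".

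**Consequences in the per-protocol (PP) set.** Appendix A no. 8 reads "Overall compliance during the double-blind treatment period <80% of the prescribed drug" and leads to complete exclusion of the subject. Appendix A no. 10 concerns "CIMT data from ultrasound scans taken more than 31 days after the last dose of study medication" and is only partial: the affected visit and later ones are dropped.

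**Timing of return.** Protocol 3.9 requires a subject taken off product to attend the Early Termination (ET) visit and hand back all medication. On timing, protocol 4.2.11 says "an attempt will be made to conduct an Early Termination (ET) Visit within 1 week of discontinuation of study treatment".

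**Role of the set.** Protocol 8.5.7 names the PP analysis as the robustness check on ITT. SAP 4.3.4 treats the ITT results as definitive, and SAP 4.6.3 keeps every scan in ITT whatever its timing relative to the last dose.

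**The concern.** The formula and the period it claims to cover have different end dates. For a subject who stops permanently, the days between the last dose and the hand-back of tablets enter the denominator with nothing in the numerator. Compliance then mixes adherence while on drug with the delay before tablets came back, and no. 8 treats the mixture as non-adherence.

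At stake is the consistency of the PP rules. No. 10 already deals with scans after a permanent stop, and does so proportionately. No. 8 can remove the same subject entirely, including scans taken on drug and scans inside the 31 days that no. 10 allows. The documents foresee such delays. The ET visit within a week is only an attempt, protocol 3.9 mentions subjects off treatment for 2 weeks or longer, and no. 10 exists because some scans may come more than 31 days after the last dose.

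**Working it through.** The documents give no worked compliance figure, so there is nothing to reproduce. I applied the 4.2.5.3 formula directly.

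**Inputs.** From the documents: one tablet daily (protocol 7.2); 80% threshold (Appendix A no. 8); on-treatment scans at weeks 26, 52 and 78, that is days 182, 364 and 546; ET visit attempted within 7 days. Assumed, because the documents do not give them: adherence on drug *a* from 0.82 to 1.00, and gap *G* from last dose to last return of 7 to 98 days. *T* is days on drug. The one-day inclusive count is ignored.

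**Formula.** Compliance under the SAP = 100 × a × T / (T + G). It falls below 80% when G > T × (a/0.8 − 1). Ended at the last dose, compliance is 100 × a whatever the gap.

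**Gap (days) that must be exceeded to fall below 80%:**

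| Stop | a = 1.00 | 0.90 | 0.85 | 0.82 |
|---|---|---|---|---|
| Week 26 (T = 182) | 45.5 | 22.8 | 11.4 | 4.5 |
| Week 52 (T = 364) | 91.0 | 45.5 | 22.8 | 9.1 |
| Week 78 (T = 546) | 136.5 | 68.2 | 34.1 | 13.6 |

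**ET visit on time (G = 7), week-26 stop.** 182/189 = 96.3% at full adherence, 86.7% at a = 0.90 and 81.9% at a = 0.85. All stay in the PP set. A 7-day gap causes failure only for T < 28, 56 or 112 days respectively, before any on-drug scan is due. At a = 0.82 it does so up to T < 280 days, which reaches subjects with a week-26 scan.

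**Long gap: stop just after one visit, tablets returned 91 days later.**

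| Stop to return | a = 1.00 | a = 0.90 |
|---|---|---|
| Week 26 to 39 | 182/273 = 66.7%, out | 60.0%, out |
| Week 52 to 65 | 364/455 = 80.0%, kept | 72.0%, out |
| Week 78 to 91 | 546/637 = 85.7%, kept | 77.1%, out |

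If the week-65 return is 7 days late, full adherence gives 364/462 = 78.8% and the subject is out.

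**Inside the 31-day window of no. 10.** With a = 0.90, a week-26 stop and return 28 days later: 0.9 × 182/210 = 78.0%. With a = 0.85, a week-52 stop and the same gap: 0.85 × 364/392 = 78.9%. In both cases no. 10 would keep a scan at the return visit, yet no. 8 removes every scan.

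**Unreturned tablets.** Assume a 91-tablet kit dispensed on day 182 and never returned, a stop on day 200, and a last visit on day 273.
- Fully adherent to day 182: (182 + 91)/273 = 100%. Had the unused tablets been returned: 200/273 = 73.3%.
- Only 91 tablets taken by day 182: (91 + 91)/273 = 66.7%.
- Shortening the denominator alone turns these two non-return figures into 273/200 = 136.5% and 182/200 = 91.0%. The second subject would wrongly enter the PP set.
- Also capping the kit's credit at 200 − 182 = 18 tablets gives 200/200 = 100% and (91 + 18)/200 = 54.5%.

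**The case against.** The strongest points on the other side are these.

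- **The planned gap is about a week.** Tablets must be returned at the ET visit, and at that gap the effect is negligible. This stands. It confines the point to late returners.
- **Late stops need very long gaps at full adherence.** This stands too: a subject who took every tablet to week 78 needs more than 136 days.
- **Silent stopping is non-compliance.** No. 8 refers to the prescribed drug, and a subject who stops unannounced has missed doses prescribed up to the next visit. The protocol's own formula in 7.5 also counts days between visits. This is a tenable view of adherence, but it is not the period the SAP names in 4.2.5.3 and no. 8 and defines in 4.6.1. No. 10 already limits what such a subject contributes after stopping.
- **A rationale may be redacted.** The amendment history says the compliance calculation was added to the table of changes from protocol, which is blacked out. I therefore do not count the departure from the protocol's by-visit rule as an error. The mismatch within the SAP remains.

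A reader might infer that the non-return sentence is what penalises early stoppers. It does not. Unreturned tablets are not subtracted, so that rule tends to hide off-drug time.

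**Conclusion.** The point holds in limited form. SAP 4.2.5.3 and Appendix A no. 8 claim to measure compliance over a period ending at the last dose, but the formula ends at the last return. For late returners this can turn acceptable on-drug adherence into complete PP exclusion, and at 85% to 90% adherence it can do so within the 31 days allowed by no. 10.

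The gap must exceed about 45 days (week-26 stop) or 91 days (week-52 stop) at full adherence, and about 23 or 46 days at 90%. These thresholds rest on a constant assumed adherence and a single final return of all unused tablets. The documents give neither the distribution of gaps nor the number of early stoppers, so the number of subjects or scans lost cannot be calculated.

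Three stronger readings are not supported:
- **Early stoppers in general lose their scans.** Those with an on-drug scan who are seen within about a week do not, unless adherence is only just above 80%.
- **No. 8 always overrides no. 10.** A fully adherent week-26 stopper with a 31-day gap scores 182/213 = 85.4% and stays in.
- **The primary result is affected, or one arm loses more subjects.** ITT uses every scan, and nothing in the documents shows that return gaps differ by arm.

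**What to change.** 1. Set the denominator to last dose date minus first dose date plus 1. This is the exposure duration in SAP 4.2.5.1, not the variant that excludes interruptions, so temporary interruptions still count as missed doses.
2. For any kit not returned, or with a missing return count, credit at most one tablet per day from dispensing to the last dose date. Without this, the shorter denominator inflates compliance for non-returners.
3. Leave scans after a permanent stop to Appendix A no. 10, so that no. 8 measures adherence on drug only and 4.2.5.3 agrees with 4.6.1.

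The cost is a short SAP text change and a revised derivation from dates and counts already collected, made before unblinding. The small downside is reliance on the recorded last dose date.

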4.3 Efficacy analysis

CIMT Data

In this study the CIMT data has a hierarchical (or multilevel) structure. The levels for the data are defined by 1) the study participants and 2) carotid artery sites within the participants. The repeated measure is time.

A multi-level, linear mixed-effects model will be used for the primary analysis to assess the difference in the annualized rate of change in the CIMT measurements across 12 carotid artery sites between rosuvastatin 20 mg and placebo treatment over 104 weeks. The model is specified in terms of fixed effects for randomized treatment group, time, time by treatment interaction, ICVD risk stratification (<5%/5%-10%) – based on IxRS data, carotid artery site,

age, sex, centre, and scan reader (In the unlikely event that the model does not converge it may be necessary to drop fixed effects for reader, sex and age in that order). Random effects within the model are the intercept and slope for individual subjects. Time in the model is a continuous measure and is the interval in years from date of randomization to date of CIMT measurement and its effect is linear.

4.3.1 Estimates of effects and tests of statistical significance for trial objectives

Between-group comparisons

In the analysis, let β_1 and β_2 represent respectively the coefficient parameters for time and time by treatment interaction in the mixed effects model. The dependent variable is maximum CIMT.

The annualized rate of change (slope) in MeanMax CIMT in placebo will be estimated by the coefficient parameter β_1 , the annualized rate of change (slope) in MeanMax CIMT in the rosuvastatin group will be estimated by $\beta_1 + \beta_2$, and the difference of annualized rate (slope) of change between 2 groups will be estimated by β_2 . Then, the null and the alternative primary hypotheses can be expressed as

$H_0: \beta_2=0$ vs. $H_a: \beta_2 \neq 0$ at a significance level of $\alpha=0.05$.

In other words, the change in MeanMax CIMT from time zero, measured in mm per year, can be estimated from the model as β_1 (Time) for the placebo group and β_1 (Time) + β_2 (Time x Treatment) for the rosuvastatin group. The estimate of the absolute difference in mm in MeanMax CIMT at 2 years between the treatment groups is β_3 (Treatment) + $2 \beta_2$ (Time x Treatment) and change from baseline at 2 years is $2 \beta_2$ (Time x Treatment).

The treatment effect is based on the Time x Treatment term and represents the difference in slopes in mm/year. The between-group test of statistical significance is the p-value associated with this term in the model.

Further details of the analyses and model are given in the following sections.

